1. STUDY SUMMARY

TITLE	Exploring the physiological role of propionate in glucose homeostasis in man.
AIMS	To investigate the effect of propionate on pancreatic beta cell and determine the impact of diabetes risk on this function.
DESIGN	
Study 1 Pharmacokinetic study: we will determine the pharmacokinetic profile of orally delivered sodium propionate in healthy volunteers in order to determine time to peak plasma concentration of orally administered propionate. Initially a dose ranging study will be conducted followed by a full pharmacokinetic profile.
 
Study 2 Dose finding study: In an open label study we will determine the most dose dependently determine the role of sodium propionate on beta cell function in healthy volunteers using oral glucose tolerance tests.
 
Study 3 How does sodium propionate improve glucose tolerance: we will determine the mode of action of propionate on improving glucose tolerance by performing acute intravenous glucose tolerance tests in both healthy volunteers and healthy volunteers at risk of developing diabetes, i.e people with impaired fasting glucose (between 5.5-7mmol/l) and HbA1C between 5.7% and 6.5%.

ELIGIBILITY	
Study 1: Healthy men and women aged between 18 and 70 years with BMI between 20-25 kg/m² and with normal fasting blood glucose (below 5.5mmol/l and HbA1C less than 5.7% will be eligible to volunteer.
 
Study 2: As for Study 1.
 
Study 3: Cohort 1: Healthy volunteers aged between 30 to 70 with a BMI between 25-35 kg/m² who do not have impaired fasting glucose and have HbA1c below 5.7%.
 
Cohort 2: Healthy volunteers aged between 30 to 70 years with a BMI between 25-35 kg/m² who have impaired fasting glucose (between 5.5-7mmol/l) and HbA1C between 5.7% and 6.5%,

ENROLMENT	
For all studies: Participants will have an initial telephone interview to assess suitability for the study. If suitable the participant will be sent the study information sheet and a date for their enrolment visit agreed. Provision of the information sheet will be no less than 24 hours before the enrolment visit. At the enrolment visit the following measurements of blood pressure, an ECG and a blood test (for full blood count, urea and electrolytes, liver function tests, lipid profile, fasting glucose, HbA1C) will be taken. In addition, a general medical and social history will be taken. All female volunteers will

undergo a pregnancy test and will be informed that they should not plan to become pregnant whilst participating in the study.

TREATMENT	Participants in the Intervention groups will receive enteric coated capsules containing sodium propionate. Participants in the Control group will receive sodium chloride in the same capsule formulation. For each study one dose per visit will be taken.
DURATION	
Study 1: Individuals participating in the dose ranging study will be asked to attend our clinical trials unit on a single day for a total of 8 hours. Volunteers taking part in the full pharmacokinetic study will be asked to attend the clinical trials unit twice for a total of 8h at each visit.
 
Study 2: Individuals will be asked to attend the clinical trials unit on 5 separate occasions each visit lasting 4 hours during which oral glucose tolerance testing will take place.
 
Study 3: All participants will be asked to attend the clinical trials unit to undertake an oral glucose tolerance test in order to screen for impaired glucose tolerance. Individuals will be asked to attend the clinical trials unit on two separate occasions each visit lasting 4 hours for the main part of the study.

MEASURES	
Study 1: The primary outcome will be peak plasma concentration of propionate coupled with determination of the elimination profile. Secondary outcomes will aim to understand the acute effects of propionate and will include plasma insulin, glucagon like peptide-1 (GLP-1), peptide yy (PYY), leptin, glucose and free fatty acid concentrations following propionate administration.
 
Study 2: Our primary outcome will be the insulinogenic index which is the increase in plasma insulin from 0-30mins during an oral glucose tolerance test. Secondary outcomes will be plasma concentrations of insulin, Glp-1, free fatty acids, PYY, leptin, glucose and free fatty acids will be measured during the oral glucose tolerance test.
 
Study 3: The primary outcome will be measurement of beta cell function as determined by the calculation of acute insulin response to glucose (the incremental area under the insulin profile from 0-10minutes following an intravenous glucose bolus) during an intravenous tolerance test.
 
Secondary outcomes will be plasma concentrations of insulin, GLP-1, PYY, Leptin glucose and free fatty acids.

2. INTRODUCTION

The NHS is estimated to spend £1million per hour (~ 10% of its yearly budget) treating diabetes and its complications. Despite advances in detection and treatment, the incidence of the disease is spiraling. Some 2.3 million people in the UK are already diagnosed and the estimated number of diagnosed and "hidden" cases of diabetes is expected to top 4 million by 2025. In those with pre-diabetes and high-risk groups, the progression towards diabetes is marked by deterioration in the function of beta-cells, the cells in the pancreas which secrete insulin in response to glucose. Maintaining tight regulation of plasma glucose by supporting beta cell function in diabetics has been shown to prevent the development of complications caused by long term hyperglycaemia. There is an urgent need for well tolerated oral therapies. We have identified a novel neutraceutical target, the short chain fatty acid (SCFA) propionate, for the prevention of diabetes in high risk groups. We aim to develop an enteric capsulation formulation to deliver propionate to the small intestine and determine its efficacy in the treatment of diabetes in man.

Short chain fatty acids.

The majority of ingested nutrients are digested by intestinal enzymes and absorbed in the upper gastrointestinal tract. However, in the colon, non-digestible carbohydrates (NDC's), which are resistant to small intestine enzymes, are digested by the colonic microbiota. Fermentation of these carbohydrates produces short chain fatty acids (SCFA), carboxylic acids with a chain length under six carbon atoms. The most abundant forms of SCFA are acetate, propionate and butyrate. A number of studies have shown that dietary supplementation with the naturally occurring NDC's inulin and oligofructose increases satiety, promotes weight loss and improves glucose homeostasis, in both animals and humans. However, the amount of NDC required to robustly produce this effect in man is associated with adverse gastrointestinal symptoms which lead to poor compliance.

How do SCFA's regulate glucose homeostasis?

Dietary NDC's are fermented by gut microbiota to produce SCFAs in the colon 10. Propionate increases the expression and release of the gut peptide glucagon like peptide-1 (GLP-1) in animals and humans. GLP-1 is a potent incretin, it has therefore been hypothesised that NDC's increase glycaemic control via the production of SCFA's in the colon. Recently, two orphan G-protein coupled receptors (GPCRs), free fatty acid receptors 2 and 3 (FFAR2 and FFAR3) have been shown to bind SCFA's. Localisation data suggests FFAR2 is the receptor which mediates SCFA release of gut hormones. However, our pilot data has suggested that propionate may also have a direct effect on the pancreas and beta cell function.

Propionate improves glucose stimulated insulin release from the beta cell.

Our preliminary data indicates the SCFA propionate augments glucose-stimulated insulin release from perfused mouse and human islets. We have also demonstrated that during intraperitoneal glucose tolerance tests (i.p. GTT) propionate improves glucose tolerance and significantly increases first phase glucose-stimulated insulin release. These findings suggest propionate may act both directly on the islet to increase insulin release and indirectly by

stimulating the release of the incretin GLP-1 from the gut. Propionate is therefore an ideal emerging target for the control of glucose homeostasis. Drugs designed to target FFAR2 are currently in development by a number of pharmaceutical companies but a drug suitable for use in man is likely to be at least ten years from production.

Propionate and glucose control in Man.

One attractive avenue for the treatment of diabetes is the use of dietary modification using existing natural substances, for example SCFA's. This strategy has the potential to be well tolerated, to achieve patient benefit in a shorter timeframe and be more cost effective than traditional pharmaceuticals. Sodium propionate exhibits very low toxicity levels in man. It is widely used in the food industry as a preservative (E281) in bread, cakes, pastries and cheese. In man propionate has been shown to be effective at improving glucose tolerance. Seven weeks of dietary supplementation with 7.5g of sodium propionate, delivered via an orally administered capsule, has been shown to decrease fasting serum glucose and maximum insulin increments during a glucose tolerance test in healthy human volunteers. Additionally, oral sodium propionate (3g/day) delivered in the diet via bread has been shown to improve plasma glucose disposal in a meal tolerance test both acutely and following one week of dietary supplementation. Our group has also demonstrated that the addition of 3g of sodium propionate to the diet decreases post prandial glucose following a high carbohydrate meal. These studies clearly demonstrate sodium propionate is well tolerated and effective at improving glucose handling in man. However, sodium propionate is very unpalatable indicating the only clinically viable route of administration is via capsule formulation. This would avoid the issue of palatability and be economically viable for widespread nutritional usage.

Design of enteric coated capsules for the delivery of propionate to the small intestine.

To overcome the very unpalatable taste of sodium propionate we developed a partnership with the Department of Chemical Engineering (CE) at Imperial College. This resulted in the development of a simple nutritional supplement based on a Hydroxypropylmethyl cellulose capsule (HPMC). HPMC capsules can be coated with enteric films which prevent gastric digestion and deliver drugs to targeted parts of the small or large bowel. For example, the enteric coating Eudragit® L 30 D-55 predominantly dissolves in the small bowel whereas Eudragit® FS 30 D-coated capsules dissolve in the proximal colon. Recently, we designed a simple encapsulation methodology to facilitate the delivery and the absorption of short chain fatty acids to the small intestine. The emulsified fatty acid is contained within an HPMC capsule with a Eudragit® L 30 D-55 coating which is resistant to the low pH's found in the stomach. We will use this delivery system to determine the effect of sodium propionate on beta cell function in man.

3. STUDY DESIGN

Consenting and Enrolment, all studies:

Volunteers will be recruited by advertising e.g posters, printed media and by approaching volunteers from previous studies who have given consent to be approached for recruitment to subsequent studies.

Potential participants will have a brief telephone interview to assess their suitability. Subsequently eligible participants will be sent the patient information sheet. Having read the patient information sheet and if they wish to continue with the enrolment process volunteers will be asked to attend the Hammersmith campus for a brief interview where any concerns regarding the study can be addressed and formal consent taken. Participants will then be eligible to begin the screening process for each study.

Study 1

Aim: To calculate the pharmacokinetic profile of orally administered sodium propionate in healthy volunteers in order to determine time to peak plasma concentration.

Study methodology: Participants will first undergo a dose ranging study where they will be given a single dose of encapsulated sodium propionate. The plasma concentration profile of sodium propionate will be used to inform the design of a full pharmacokinetic profiling study. In this study participants will receive a low dose of sodium propionate and a second higher dose a week later.

Participants: 6 male or female volunteers, age 18-70 years, BMI 20-25 kg/m², with normal fasting glucose and HbA1C. Screen failures will be replaced.

Health Screening and enrolment Visit

Participants will arrive fasted from 8pm the previous evening. They will be clerked and examined by a research doctor. Measurements of height, weight, body fat content, blood pressure, an ECG and a blood test (for full blood count, urea and electrolytes, liver function tests, lipid profile, fasting glucose, HbA1C) will be taken. Screen failures will be replaced.

Dose ranging Study

Participants will arrive at the St John McMichael Centre (Hammersmith Hospital) on the day of the study having fasted from the previous evening. A canulae will be inserted into a peripheral vein and blood samples (10ml) will be taken at -10, 0, 15, 30, 60, 90, 120, 150, 180, 4h, 6h, 8h post administration of an oral dose of propionate (3g). Total volume of blood removed will be 120mls.

Pharmacokinetic profiling Study

Study Day1: Using the data from the dose ranging study a full pharmacokinetic study will be undertaken. Participants will arrive at the St. John McMichael Centre (Hammersmith

hospital) having fasted from the previous evening and a canulae will be inserted into a peripheral vein. Blood samples (10ml) will be taken at -10 and 0 post oral propionate administration (3g) then 4 samples will be taken during each of the absorption and early elimination phases, followed by further samples post peak for a total of 6 samples in this phase, over three half-lives. In total 120mls of blood will be drawn.

Study Day 2: At least a week following the first study day participants will be asked to attend a repeat visit at the St John Mc Michael Centre which will follow the same protocol as for study day 1 but participants will be given a 6g dose of propionate.

Blood samples will be analysed using the following methods:

- Propionate by Mass spectrometry
- Insulin, GLP-1, PYY, leptin and non-esterified fatty acids will be measured using commercially available kits.
- Glucose will be measured using a glucometer.

Study 2

Aim: To dose dependently determine if propionate augments beta cell function.

Study methodology: Participants will undergo a series of oral glucose tolerance tests (OGTT) following administration of propionate. Each participant will receive all doses of propionate and each study day will be separated by at least 1 week.

Participants: 30 healthy men and women aged 18-70, body mass index (BMI) 20-25 kg/m², with normal fasting glucose and HbA1C.

Support for number of participants: A previous small study of the effects of propionate on glucose levels in humans identified a 47.4% reduction in glucose AUC over 2 hours following consumption of a standard 50 g carbohydrate load supplemented with propionate. Mean OGTT glucose AUC in a group of 514 healthy subjects was 40.8 mmol.min (SD 7.1 – unpublished data from the study described in Diabetic Medicine 2007;24:1269-1278). A 47.4% reduction in OGTT glucose AUC would result in a mean glucose AUC of 21.5. Using data from the same study, a mean insulinogenic index of 0.99 (SD 0.85) was observed, regression analysis estimated that a 47.4% reduction in glucose AUC would be associated with an increase in insulinogenic index of 0.73 SD. This can be detected as significant at p<0.05, with 80% power using 30 in each group. Screen failures will be replaced.

Health Screening and enrolment Visit

Participants will arrive fasted from 8pm the previous evening. They will be clerked and examined by a research doctor. Measurements of height, weight, body fat content, blood pressure , an ECG and a blood test (for full blood count, urea and electrolytes, liver function tests, lipid profile, fasting glucose, HbA1C) will be taken. Screen failures will be replaced.

Study Day 1-5 Participants will undergo a frequently sampled oral glucose tolerance test (OGTT) to detect changes in insulin sensitivity and beta cell function. Participants will be asked to refrain from strenuous exercise and alcohol on the day prior to each study. They will be asked to eat a standard meal of your choice before the study (e.g. ready-made meal) and then be required to fast overnight.

They will be asked to come to the Clinical Investigations Unit at Hammersmith Hospital at 8:30am, having fasted from 8pm the previous day. A small plastic tube (cannula) will be inserted into their arm and a blood sample taken. This will be in place for the duration of the study day. Baseline blood samples will be taken at -30 and -10mins before the participant will take capsules containing either sodium chloride (placebo control) or sodium propionate. They will then consume a 250 ml drink containing 75 g of glucose at a pre-determined time so that the expected peak blood glucose level coincides with the expected peak propionate blood concentration. During the next 3 hours they will have blood samples taken at 0, 10, 20, 30, 60, 90, 120, 180 mins after the glucose drink. A total of 90 ml of blood will be taken (about 6-8 tablespoons of blood). These will be taken through the cannula. After 3 hours the cannula will be removed and the participant will be provided with a light snack and able to go home.

Participants will be asked to attend four repeat visits with a minimum of a week between visits. They will randomly be assigned an oral dose of propionate, either 0, 1, 3, 6, 9g.

Blood samples will be analysed using the following methods:

- Propionate by Mass spectrometry
- Insulin, GLP-1, PYY, leptin and non-esterified fatty acids will be measured using commercially available kits.
- Glucose will be measured using a glucometer.

Study 3

Aim: To determine the effect of propionate on beta cell function using the gold standard intravenous glucose tolerance (IVGTT) test in healthy participants and healthy volunteers at risk of developing diabetes.

Study methodology: Participants will undergo intravenous glucose tolerance tests. The effect of propionate on beta cell function will be determined in a randomised double blind placebo controlled crossover study.

Participants:

Cohort 1: 34 healthy men and women aged 30-70, body mass index (BMI) 25-35 kg/m², normal fasting blood glucose (below 5.5mmol/l and HbA1C less than 5.7% will be eligible to volunteer. Screen failures will be replaced.

Cohort 2: 34 men and women at risk of developing diabetes aged 30-70 with a body mass index (BMI) 25-35 kg/m² with fasting blood glucose between 5.6mmol/l and HbA1C between 5.8 and 6.5% will be eligible to volunteer. Screen failures will be replaced.

Support for number of participants: Our pilot data demonstrates mean Insulin AUC₁₀ of 8.1 for saline treated mice versus 11.3 for mice propionate-treated mice, an increase in the acute insulin response to glucose of 40%. Mean IVGTT-AIRg in a group of 306 healthy subjects was 492 mU.min (SD 48.7 - unpublished data from the study described in Diabetologia 2004;47:1157-1166). Using log-transformed data for IVGTT-AIRg, it was estimated that a 40% increase in IVGTT-AIRg would constitute an increase of 0.79 SD, which could be detected as significant at p<0.05, with 90% power using 34 in each group. Screen failures will be replaced.

Health Screening and enrolment Visit

Participants will arrive fasted from 8pm the previous evening. They will be clerked and examined by a research doctor. Measurements of height, weight, body fat content, blood pressure, an ECG and a blood test (for full blood count, urea and electrolytes, liver function tests, lipid profile, fasting glucose, HbA1C) will be taken. Screen failures will be replaced.

Visit 1: Oral glucose tolerance test.

The participant will be asked to come to the Clinical Investigations Unit at Hammersmith Hospital at 8:30am, having fasted from 8pm the previous day. A cannula will be inserted into a peripheral vein and two fasting blood samples taken at -30 and -10 mins before the participant consumes a drink containing 75 g of glucose. During the next 3 hours blood samples will be taken at 0, 10, 20, 30, 60, 90, 120, 180 minutes post glucose administration. A total of 100ml of blood will be taken.

Visit 2 and 3: Participants will undergo a frequently sampled intravenous glucose tolerance test (IVGTT) to detect changes in insulin sensitivity and beta cell function. The day prior to the study subjects will be asked to refrain from alcohol and strenuous exercise and fast for 12 hours prior to the study. The study will be carried out at the St. John Mc Michael Centre (Hammersmith hospital). Subjects will have two cannulae placed in separate peripheral veins. Subjects will be given glucose (20% solution-0.3g/kg) directly into a peripheral vein following oral administration of propionate at the most effective dose determined in study 2. Timing of the glucose bolus will be determined from data gathered in study 1 and be given 5mins prior to the expected plasma peak concentrations of sodium propionate. Blood samples (10ml) will be taken at, -5, 0, 2, 4, 6, 8, 10, 19, 22, 30, 40, 50, 70, 100 & 180 where glucose is administered at time 0, in total 150ml of blood will be drawn. Participants will be administered human insulin (0.03units/kg, 'regular human insulin – Novo Nordisk') at 20 mins post glucose. Participants will be asked to attend a repeat visit with a minimum of a week between visits. Participants will be randomly assigned propionate or placebo.

Blood samples will be analysed using the following methods:

- Propionate by Mass spectrometry

- Insulin, GLP-1, PYY, leptin and non-esterified fatty acids will be measured using commercially available kits.
- Glucose will be measured using a glucometer.
-

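### Study 2's sample-size paragraph gives a glucose AUC that cannot be a total AUC in its stated unit, quotes a two-group power for a crossover, and rests on a thinly supported 0.73 SD effect

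*Combined protocol and SAP*

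**What the plan says.** All of the sample-size reasoning is in section 3 (Study Design), Study 2, in the paragraph supporting the number of participants.

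- A small earlier study "identified a 47.4% reduction in glucose AUC over 2 hours following consumption of a standard 50 g carbohydrate load supplemented with propionate".
- The reference data: "Mean OGTT glucose AUC in a group of 514 healthy subjects was 40.8 mmol.min" ("SD 7.1 – unpublished data from the study").
- The two combined: "A 47.4% reduction in OGTT glucose AUC would result in a mean glucose AUC of 21.5".
- The outcome scale: "a mean insulinogenic index of 0.99 (SD 0.85) was observed".
- The conversion: "regression analysis estimated that a 47.4% reduction in glucose AUC would be associated with an increase in insulinogenic index of 0.73 SD".
- The power claim, at p<0.05: "with 80% power using 30 in each group".

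The same section describes 30 participants in total, each taking every dose level (0, 1, 3, 6 and 9 g) at visits at least a week apart, with 3 hours of sampling after a 75 g glucose drink. Section 7 plans t-tests for two groups and ANOVA for three or more. The paragraph does not say whether either glucose AUC is total or incremental, does not give the time window of the reference AUC, and reports no slope, standard error or observed range for the regression.

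**The concern.** The power claim depends on one number, the 0.73 SD effect, and each step leading to it raises a question. The reference AUC is far too small for a total glucose AUC in mmol.min. The percentage reduction comes from one study and the mean from another, and a percentage carries over between AUCs only if both are of the same kind. The implied fall is very large relative to the spread of the reference data. The final power formula is for separate groups, which is not the Study 2 design.

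The insulinogenic index is Study 2's primary outcome, and Study 3 takes its dose from Study 2. If Study 2 shows no clear effect, readers will turn to this paragraph to judge whether a worthwhile effect was missed. As written, it cannot tell them.

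**Working it through.** **Inputs from the protocol.** Reference glucose AUC mean 40.8, SD 7.1, 514 subjects; reduction 47.4%; index mean 0.99, SD 0.85; effect 0.73 SD; 30 per group; p<0.05 (two-sided reproduces the claim). Normal fasting glucose is below 5.5 mmol/l (section 4).

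**Assumed, not in the protocol.** Within-person correlation ρ of 0.3 to 0.7; 30 complete pairs; normally distributed AUC where stated; illustrative AUC falls of 10% and 20%.

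**1. The plan's own figures.**
- 40.8 × (1 − 0.474) = 21.46, stated as 21.5.
- Two-sample comparison, d = 0.73, 30 per group, two-sided 0.05: 80.7% (normal approximation) or 79.4% (noncentral t). The 80% reproduces.

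**2. The unit.**
- 40.8 / 120 min = 0.34 mmol/l; 40.8 / 180 min = 0.23 mmol/l.
- A flat 5.5 mmol/l for 120 min would give 5.5 × 120 = 660.
- Reading the figure as mmol/l × hours gives 40.8 / 2 = 20.4 or 40.8 / 3 = 13.6 mmol/l on average, implausibly high for healthy subjects.
- As an incremental AUC it would be a mean rise of only 0.34 mmol/l over 2 hours. The documents do not strictly exclude this.

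**3. Whether 47.4% can be applied to 40.8.** If 40.8 is a total AUC in some other unit, a 47.4% cut leaves average glucose at or above fasting only if untreated glucose averages at least 1 / (1 − 0.474) = 1.90 times fasting. That is a reason to ask about AUC type; it does not prove a mismatch.

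**4. Size of the extrapolation.**
- Shift: 0.474 × 40.8 / 7.1 = 2.72 SD.
- If AUC is normally distributed, 514 × Φ(−2.72) ≈ 1.7 subjects lie that low.
- Implied slope, if linear: 0.73 / 2.72 = 0.27 SD of index per SD of AUC.
- On the index scale: 0.73 × 0.85 = 0.62, taking 0.99 to 1.61.

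**5. Power of the actual design at the plan's 0.73 SD.** For one paired comparison, the standardised difference is d_z = d / √(2(1 − ρ)), n = 30, two-sided 0.05, noncentral t:

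| ρ | d_z | power |
|---|---|---|
| 0.3 | 0.62 | 90% |
| 0.5 | 0.73 | 97% |
| 0.7 | 0.94 | 99.9% |

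**6. Illustration of smaller falls, using the implied slope.** d = 0.268 × (fall × 40.8 / 7.1):

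| AUC fall | d | two-group formula | paired, ρ = 0.3 to 0.7 |
|---|---|---|---|
| 10% | 0.15 | 9% | 11–18% |
| 20% | 0.31 | 22% | 28–56% |
| 47.4% (plan) | 0.73 | 79% | 90–99.9% |

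**7. What 30 people deliver as a crossover, at 80% power.**
- One dose against placebo, two-sided 0.05: d_z = 0.53. Multiplying by √(2(1 − ρ)) gives 0.63 between-person SD at ρ = 0.3 and 0.41 at ρ = 0.7.
- Four active doses against placebo, Bonferroni 0.05 / 4 = 0.0125: d_z = 0.64, or 0.76 to 0.50 between-person SD over the same correlations.

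**The case against.** The strongest reply is that nothing in the power arithmetic is wrong. The 47.4%, the 2.72 SD and the 0.73 SD are all unit-free, so a mislabelled AUC changes none of them, and 0.73 SD with 30 per group does give 80%. That stands. A reader might infer that the unit error invalidates the power; it does not. It shows that the reference figure was not reported correctly or completely.

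A reader might also infer that an incremental reduction was applied to a total AUC and that the effect is therefore several times too large. The documents label neither figure, so this is conjecture. What stands is that the plan does not show the two to be alike.

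The extrapolation argument has limits too. The count of about 2 in 514 assumes normality, and the observed range is not given. The 10% and 20% falls come from no part of the protocol, and they assume a straight line through zero on a scale that the plan does not specify.

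Finally, for a single comparison at ρ of 0.3 to 0.7, the two-group formula understates the power of a crossover at the plan's own effect. That stands, and it rules out the claim that Study 2 has been shown to be underpowered.

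**Conclusion.** The paragraph is wrong as written on two counts and weakly supported on a third.

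1. **AUC figure.** 40.8 mmol.min cannot be a total glucose AUC in that unit, and the kind of AUC is missing for both it and the 47.4%. This needs no assumption beyond the protocol's fasting limit.
2. **Power figure.** The 80% is not the power of Study 2's design. At 0.73 SD, a single paired comparison has about 90% to 99.9% power for assumed correlations of 0.3 to 0.7.
3. **Effect size.** The 0.73 SD is an association across reference subjects, applied at a 2.72 SD fall and read as a treatment effect, with no slope or precision reported. It is poorly supported, but not shown to be false. The low powers for 10% and 20% falls show only how sensitive the claim is to this input.

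The tempting conclusion that 30 participants are too few does not follow. The documents do not establish the true effect or the within-person correlation. The plan does not yet tell the reader what 30 participants can detect.

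**What to change.** Revise the Study 2 sample-size paragraph as follows.

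- Correct the reference AUC value or its unit, give its type and time window, and confirm that the 47.4% refers to the same type and window. If it does not, stop applying it to that mean.
- Keep n=30 and replace the two-group 80% statement with the crossover figure: 80% power for 0.53 SD of the within-person differences for one dose against placebo at two-sided 0.05. Give the equivalent of 0.41 to 0.63 between-person SD, naming the assumed correlation of 0.7 to 0.3.
- Say how the four active doses are handled. With Bonferroni adjustment the detectable difference is about 0.64 SD of the differences.
- Present 0.73 SD only as one scenario in a range, with the regression slope, its precision and the observed AUC range if it is kept.

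The cost is rewording one paragraph, plus a look back at the reference data. No extra participants or visits are needed.

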7. STATISTICS AND DATA ANALYSIS

An independent researcher (i.e. not linked to the study) will be given the task of randomisation, which will be by sealed envelopes.

Although the data handling and statistical methodology can only be confirmed once all the data is collected. Our intention is to use parametric techniques to analyse the data if it is normally distributed. We will therefore use T-tests for comparisons between two groups and ANOVA for comparisons of three or more groups.

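### Study 2's 80% power is for one unadjusted, unpaired comparison, and the stated analysis does not control error when saying which of four doses works

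*Combined protocol and SAP*

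**What the plan says.** Section 3, Study 2, recruits "30 healthy men and women aged 18-70" and describes a within-person design: "Each participant will receive all doses of propionate and each study day will be separated by at least 1 week". The levels appear under Study Day 1-5: "They will randomly be assigned an oral dose of propionate, either 0, 1, 3, 6, 9g". The Study Summary makes the insulinogenic index the primary outcome.

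The sample-size paragraph starts from reference data in which "a mean insulinogenic index of 0.99 (SD 0.85) was observed". It then argues that "a 47.4% reduction in glucose AUC would be associated with an increase in insulinogenic index of 0.73 SD", and concludes: "This can be detected as significant at p<0.05, with 80% power using 30 in each group".

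Section 7 is the only analysis text. It gives t-tests for two groups and "ANOVA for comparisons of three or more groups", provided the data are normally distributed. For Study 2 it names no contrast with 0 g, primary dose, testing order, trend test, follow-up procedure or multiplicity rule. Section 3, Study 3 then carries forward whichever dose Study 2 shows to be most effective.

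**The concern.** The power statement and the design describe different tests. The statement covers one contrast between two separate groups of 30. The study has four contrasts with a shared 0 g visit, all within the same 30 people. The one test that Section 7 names for five levels, the omnibus ANOVA, can show that the levels differ somewhere. It cannot show which doses differ from 0 g, and Study 2 is meant to answer its question dose by dose.

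Some dose-level comparison will therefore have to be made, and the plan gives no rule for it. Two things are at stake: how often an inert dose is reported as active, and whether the quoted 80% describes any comparison the study will report.

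**Working it through.** **Inputs from Section 3.** Effect 0.73 SD; n = 30; p<0.05; five levels, hence four contrasts with 0 g. Sidedness is not stated. A one-sided test would give 88.1%, so the plan's figure is two-sided.

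**Input assumed.** The correlation r between visits in the same person. The documents give neither r nor a within-person SD, so a range is shown.

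**1. Reproduce the plan's figure.** For two independent groups the noncentrality is 0.73 × √(30/2) = 2.827. With 58 df the two-sided critical value is 2.002.
- Noncentral t: power = 79.4%.
- Normal approximation: power = 80.7%.

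The stated 80% is therefore one unadjusted, unpaired comparison.

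**2. Error with four unadjusted comparisons and no preceding ANOVA, all doses inert.** Contrasts that share a control have correlation 0.5, so the family-wise error is

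1 − ∫ φ(x) [Φ(√2·c + x) − Φ(−√2·c + x)]⁴ dx.

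At c = 1.96 this is 15.6%; with t critical values on 116 df it is 15.5%. Simulated paired t-tests agree (about 16%).

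**3. Error when a significant ANOVA is required first.** Simulation: 30 people, five levels, 5% repeated-measures F test, then unadjusted paired tests against 0 g.

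| Truth | Chance of a false dose claim |
|---|---|
| No dose works (r = 0.5) | about 4% |
| One dose works at 0.73 SD, r = 0 | 11.9% over the three inert doses |
| Same, r = 0.3 | 12.2% |
| Same, r = 0.5 | 12.8% |

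Without the ANOVA the last figure is also 12.8%. Once one dose works, the F test is nearly always significant (98.9% at r = 0.5) and no longer restrains the other comparisons.

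**4. Error with Dunnett.** The within-person model has (30 − 1) × (5 − 1) = 116 residual df, ignoring period terms, and a two-sided critical value of 2.476. With one dose working and r = 0.5, the error over the three inert doses is about 4%.

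**5. Power for one dose with Dunnett.** The within-person noncentrality is 0.73 × √(30 / (2(1 − r))) = 0.73 × √(15 / (1 − r)).

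| r (assumed) | Noncentrality | Power at 2.476, 116 df |
|---|---|---|
| 0 | 2.827 | 63.8% |
| 0.2 | 3.161 | 75.2% |
| 0.3 | 3.379 | 81.5% |
| 0.5 | 3.998 | 93.4% |

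On the plan's independent-groups basis (145 df, critical value 2.469) the figure is 64.0%.

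**The case against.** A reader might infer a sharper dilemma: either an inert substance yields an apparently effective dose about 15% of the time, or power falls to about 64%. The documents do not support that.

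- **The 15%.** Section 7 names ANOVA for three or more groups, and Study 2 has five levels. If a significant ANOVA is required first, the error for an inert substance is about 4%. The 15-16% arises only if the ANOVA is bypassed. Section 7 does not say that the ANOVA controls later tests, so bypassing it is possible but not planned.
- **The 64%.** This keeps the independent-groups formula, while the study is within-person. Adjusted power could be below or above 80% depending on a correlation the documents do not give.

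Nor do the documents say that four pairwise tests will be run. A trend test would also address dose dependence. On the independent-groups basis, a contrast linear in dose has about 90% power if the effect rises linearly to 0.73 SD at the top level, but about 53% if all doses act equally. A fixed testing sequence would keep about 80% for its first test. Dunnett is thus one sound choice among several.

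Finally, Study 2 is an open-label dose-finding study, and Study 3 tests propionate again in a randomised double-blind crossover. Picking the numerically best dose for Study 3 does not itself need a multiplicity adjustment. That limits the consequence.

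All of this stands. It does not remove the error of about 12% when one dose works, or the absence of any rule for declaring which doses work.

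**Conclusion.** The point holds in a bounded form. The 80% describes one unadjusted comparison of two independent groups, which is not the design. The stated analysis leaves about a 12% chance of declaring at least one of three inert doses effective when the fourth works, even if the ANOVA is applied first. That applies to claims about which doses work, not to the choice of a dose for Study 3.

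The 12% rests on a 0.73 SD effect at one dose and unadjusted follow-up tests; it barely moves for r between 0 and 0.5. The adjusted power does depend on r, from about 64% at 0 to 93% at 0.5, so the documents do not fix it. All figures assume normal data, equal variances, equal correlation between visits and no dropout. This is worth correcting before analysis but does not invalidate the design.

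**What to change.** **Section 7.** For Study 2, specify contrasts of each active dose with 0 g from a within-person model, Dunnett-adjusted, with simultaneous 95% intervals. Another prespecified error-controlling procedure, such as a fixed sequence, would also serve. So would a trend test, if the claim is confined to dose dependence. Say that selecting the dose for Study 3 is a separate step from declaring which doses work.

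**Section 3, Study 2 sample-size paragraph.** State that the 80% is for one unadjusted, unpaired comparison. Restate power for the adjusted within-person contrast, giving the assumed correlation and its source; the table above gives the Dunnett values.

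**Cost.** A few sentences and one restated figure. No extra participants are proposed: at r = 0.3 or more, 30 people give over 80% under these assumptions. The downside is a stricter threshold for each dose (critical value 2.476 against about 1.98 unadjusted). If r is nearer 0.2, power is about 75%, and the plan should say so.
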